4.5.3 Exploratory Efficacy Endpoints

The exploratory efficacy endpoints are listed in Section 2.1.3. Similar to the secondary endpoints, exploratory endpoints will be summarized based on data from baseline to Week 48 at the time of the primary analysis. At the time of the final study analysis, exploratory endpoints will be evaluated based on data from baseline to Week 96.

Exploratory efficacy endpoints based on mesopic microperimetry assessments will be based on the microperimetry-analysis population; statistical inferences for efficacy endpoints based on microperimetry assessments will be based on pooled data from Studies GX29176 and GX29185. All other secondary efficacy endpoints will be based on the ITT patient population.

Analysis of exploratory endpoints is planned for the overall patient population and for each biomarker subgroup. However, similar to the secondary efficacy endpoints, analysis of the exploratory efficacy endpoints may focus on the evaluation for either the overall patient group or the biomarker subgroups depending on the primary endpoint results.

Treatment-effect related analyses to compare each lampalizumab treatment arm (Q4W or Q6W) and the pooled sham arm for exploratory efficacy endpoints will be similar to that for secondary endpoints. In general, continuous secondary endpoints will be analyzed using a MMRM analysis, with change from baseline as the response variable. Independent variables for treatment arm, study visit (categorical variable), treatment arm by study visit interaction, baseline value of the endpoint, and the randomization stratification factors and baseline covariates as described in Section 4.5 will be included in the model. An unstructured covariance matrix will be used to model the within-subject errors, and a heterogeneous compound symmetry covariance structure used if there are convergence problems.

In general, binary secondary endpoints will be analyzed using a logistic regression model. The model will include independent variables for treatment arm, baseline value of the endpoint (continuous scale), and the randomization stratification factors and baseline covariates as described in Section 4.5, as appropriate. If the response rate is low, an unadjusted analysis may be performed. Unless noted otherwise, analyses will be based on the observed data for the timepoint, with no imputation for missing data.

For the analysis of the proportion of patients with <20% increase in GA area, patients with missing GA assessment at the analysis timepoint (e.g. Week 48) will be included in the analysis and counted as having a $\geq 20\%$ increase if such an outcome was observed at any earlier timepoint.

Reading function scores will be calculated per MNRead or Radner user's manuals, with no adjustment for reading inaccuracy. For reading function endpoints (maximum reading speed, critical print size, and reading acuity), data collected via the two reading charts will be pooled for analysis and the model will include an additional covariate for reading chart type (MNRead or Radner). Additional subgroup analyses by reading chart type (MNRead or Radner) will be performed to assess the consistency of findings across the two reading charts. In addition, for analyses based on percent change in reading speed, the baseline reading speed will not be included in the model.

FRI Level will be calculated per the scoring algorithm in the FRI Index user's manual.

For analyses of binocular maximum reading speed, binocular critical print size, and binocular reading acuity, an additional adjustment for better seeing eye BCVA at baseline will be included (instead of study eye baseline BCVA [20/50 or better vs. worse than 20/50]).

In addition, the relationship between GA area and visual function outcomes (e.g. LLVA etc.) will be explored. Observed data will be used. Spearman correlation coefficient will be estimated and a 95% CI for the correlation coefficient provided.

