2.3.2 Estimated Power Based on Information from Study GX29633

The primary efficacy endpoint is the change from baseline in GA area at 1 year (48 weeks) as assessed by FAF. As specified in Section 4.5.1, the primary efficacy objectives will be assessed by analysis of the primary efficacy endpoint in the overall patient population and in the biomarker-positive group for each dosing frequency separately.

[Table 2](#) summarizes the power and minimum detectable difference for the primary endpoint analysis when evaluated for the overall patient population and the biomarker-positive group using progression rates and variability assumptions based on data from Study GX29633, a prospective epidemiological study of the progression of GA secondary to AMD (May 2017 interim analysis). Namely, calculations assumed a progression rate (mean change from baseline in GA area at 48-weeks) of 2.08 mm² for both the biomarker-positive and biomarker-negative patient groups and a SD of 1.53 mm² for the change from baseline in GA area at 48-weeks. With these assumptions, 312 patients per lampalizumab treatment arm and 156 patients per sham arm will provide 88% power to declare a difference between each lampalizumab treatment arm and the pooled sham arm in the overall patient population for a targeted difference of 0.42 mm² (approximately 20% reduction relative to sham control) in the change from baseline in GA area at 48 weeks ([Table 2](#)). Estimated power to detect specified differences in the primary efficacy endpoint within the biomarker-positive

patient population is as shown in Table 2. Calculations were based on two-sided t-tests at the $\alpha=0.0496$ level (after adjustment for the four data reviews conducted by the iDMC prior to analysis of the primary efficacy endpoint), with the assumption of a 15% dropout rate by 48 weeks.

Table 2 Power and Minimum Detectable Difference for Analysis of Primary Endpoint Using Assumptions Based on the Epidemiological Study GX29633

Endpoint Summary and Population	Target Treatment Effect	Two-Sided $\alpha=0.0496$	
		Power	MDD
Mean change from baseline in GA area at 1 year (48 weeks) in all patients (n=312 per arm)	$\Delta=0.42 \text{ mm}^2$ (approximately 20% ^a reduction) SD= 1.53	88%	0.26 mm^2 (approximately 13% ^a reduction)

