For endpoints that are defined in terms of change from baseline, patients who do not have a baseline value reported for a particular assessment will be excluded from the change-from-baseline analyses for that assessment. Similarly, in general, patients who do not have at least one post-baseline value reported for a particular assessment will be excluded from the change from baseline analyses for that assessment. For selected endpoints, sensitivity analyses that include patients without observed post-baseline values will be performed.

For continuous outcomes, a data-as-observed approach with a mixed-effect model repeated measures (MMRM) will be used to handle missing data, which assumes that the missing data are missing at random (MAR). For binary outcomes, analysis of the outcome at a specific time point will be based on observed data, unless otherwise noted. Study discontinuations and the reasons for study discontinuations will be summarized by treatment arm (see Section 4.3) to evaluate the potential impact of missing data on the results. In addition, a number of sensitivity analyses to assess the robustness of the primary analysis results to missing data assumptions will be performed.

For patient-reported outcome measures (e.g., NEI VFQ-25), there are two types of missing data: missing at the form level and missing at the item level. Missing form level data will be handled as described above. Missing item values will follow the rules for scoring and handling of missing item-level data as described in the user's manual.

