4.5.1.4 Sensitivity Analyses

Sensitivity analyses will be performed to evaluate the robustness of the primary analysis results. Analyses will be performed for the overall patient population and/or the biomarker subgroup populations, as deemed appropriate based on the outcome of the primary analyses including all patients in the ITT population.

Multiple Imputation

The following sensitivity analysis based on multiple imputation will be performed, as appropriate, using the same statistical approach as the one used in the primary analysis:

- Change from baseline in GA area as measured using FAF, with missing data imputed by multiple imputation using the Markov Chain Monte Carlo (MCMC) method assuming MAR
- Change from baseline in GA area as measured using FAF, with missing data imputed by multiple imputation using regression method assuming MAR
- Change from baseline in GA area as measured using FAF, with missing data imputed by multiple imputation using pattern mixture model method assuming missing not at random (MNAR)
- Change from baseline in GA area as measured using FAF, with missing data imputed by multiple imputation using tipping point analysis method assuming MNAR

Considering the details of the four multiple imputation methods (MCMC, regression method, pattern mixture model, and tipping point analysis) further, MCMC and regression methods assume MAR, where the imputed data will follow the same distribution as the observed data within the same treatment group. Pattern mixture model and tipping point analysis methods assume MNAR, where the imputed data for the active treatment group will follow either the distribution of the control group or adjusted by a shift parameter.

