Geographic atrophy is progressive and irreversible, so changes in GA area over time should be ≥ 0 mm². In order to incorporate this data pattern, imputation for missing data will be performed on the difference in GA area at a visit from the previous visit. Imputation for the non-monotone missing pattern (i.e., arbitrary missing pattern) will be performed prior to the multiple imputation for the monotone missing pattern (i.e., where a missing GA area measurement at a visit for a patient implies that GA area measurements at all subsequent visits for that patient are missing). For the non-monotone missing pattern, missing value(s) between two visits with measured GA area will be imputed according to a linear growth line passing through the two measured sizes. Multiple imputation will only be carried out for monotone missing pattern.

All four imputation methods will be implemented in SAS using the three standard steps to generate inference from imputed data: imputation step, analysis step, and pooling step.

1. The missing data are filled in 100 times to generate 100 complete data sets.
2. The 100 complete data sets are analyzed by using the same approach as for the analysis for the primary objective.
3. The results from the 100 complete data sets are combined for the inference.

Methods used in the imputation step are described below. The actual parameters used in all imputations will be documented in the programming specifications. Analysis and

pooling steps will be carried out following the imputation step will also be documented in the programming specifications.

- **MCMC Method.** The MCMC method will be implemented for each treatment arm (the two sham arms will be pooled) and by biomarker status.
- **Regression Method.** The regression method will be implemented for each treatment arm and by biomarker status. This method assumes MAR, and serves as the reference for the pattern mixture model and tipping point analysis methods which assume MNAR.
- **Pattern Mixture Model Method.** The pattern mixture model method will be implemented for each active treatment arm and by biomarker status. For the active treatment arms, the missing data will be imputed based on the observed values in the pooled sham arm.

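### The missing-data rule for the exploratory proportion with <20% GA growth adds missing patients back only when they have already failed, so the per-arm rate is biased slightly low even under random dropout

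*SAP*

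**What the plan says.** The endpoint is listed in SAP Section 2.1.3 among the exploratory endpoints, which are to be formally tested at Week 96. Table 3 in Section 2.4 assigns them a two-sided alpha of 0.0496.

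Section 4.5.3 gives this endpoint its own missing-data rule: "patients with missing GA assessment at the analysis timepoint (e.g. Week 48) will be included in the analysis and counted as having a" ≥20% "increase if such an outcome was observed at any earlier timepoint". Nothing is said about a patient whose image is missing and who had no earlier ≥20% increase.

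Two defaults surround the rule. Section 4.5 states: "For binary outcomes, analysis of the outcome at a specific time point will be based on observed data, unless otherwise noted". Section 4.5.3 repeats it for the exploratory binary endpoints: "Unless noted otherwise, analyses will be based on the observed data for the timepoint, with no imputation for missing data". Section 4.5 also says that, in general, patients with no post-baseline value are left out of change-from-baseline analyses.

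For the primary endpoint, Section 4.5.1.4 already contains a fuller approach. It notes: "Geographic atrophy is progressive and irreversible, so changes in GA area over time should be" zero or more. It therefore specifies that "imputation for missing data will be performed on the difference in GA area at a visit from the previous visit", with linear interpolation of intermittent gaps and, among its methods, "Change from baseline in GA area as measured using FAF, with missing data imputed by multiple imputation using regression method assuming MAR".

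**The concern.** Carrying an observed failure forward is sound when lesions do not shrink. The difficulty is what happens to the other missing patients. Under the defaults they drop out of the denominator, while missing patients who have already failed stay in it. Whether a missing patient is counted therefore depends on that patient's outcome, and every missing patient who is counted is a failure. The reported proportion with <20% growth is pulled down in each arm even when dropout has nothing to do with the disease.

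At stake is the accuracy of a descriptive responder rate that may be quoted at Weeks 48 and 96. The treatment comparison is much less exposed.

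**Working it through.** **Reproducing the plan's own figure.** The SAP gives no rate or power for this endpoint. The nearest stated figure that uses the same inputs is the 88% power in Section 2.3.2. Completers per arm: 312 × 0.85 = 265.2. SE = 1.53 × √(2/265.2) = 0.133 mm². Power at two-sided 0.0496: Φ(0.42/0.133 − 1.963) ≈ 88%. It reproduces, as does the minimum detectable difference: 1.963 × 0.133 = 0.26 mm².

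**Inputs from the documents**
- Growth over 48 weeks: mean 2.08 mm², SD 1.53 mm² (SAP 2.3.2).
- Dropout by Week 48: 15% ("with the assumption of a 15% dropout rate by 48 weeks").
- Dropout by Week 96: 25%, stated only for microperimetry (Protocol 6.1) and borrowed here.
- Baseline area 2.54–17.78 mm² (Protocol 4.1.1).
- FAF at Weeks 24, 36, 48, 72 and 96 (Protocol Appendix 1).

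**Assumptions, because the documents are silent**
- Log-normal baseline area, median 7.5 mm², log-SD 0.5, truncated to the eligible range.
- Gamma-distributed growth, unrelated to baseline area and linear in time.
- Completely random dropout, evenly timed within each year (15% in year 1, a further 10% in year 2).

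**Formulas.** Let p be the true proportion with <20% growth, m the fraction missing, and e the fraction of all patients who are missing with an earlier observed failure.
- Rule read with the defaults: p(1−m)/(1−m+e). This is never above p, and equals p when e = 0.
- Plain observed cases: p(1−m)/(1−m) = p.
- Alternative reading, in which all missing patients are included and those without an earlier failure count as <20%: p(1−m) + m − e.

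**Central case, evaluated by simulation**

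| | Week 48 | Week 96 |
|---|---|---|
| True p | 44.0% | 19.7% |
| m | 15% | 25% |
| e | 2.6% | 9.0% |
| Rule with defaults | 0.374/0.876 = 42.7% | 0.148/0.840 = 17.6% |
| Bias | −1.3 points | −2.1 points |
| Alternative reading | 0.374 + 0.124 = 49.8% | 0.148 + 0.160 = 30.8% |
| Bias | +5.8 points | +11.1 points |

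**Sensitivity of the supported reading**
- Every dropout has an early-termination FAF: more earlier failures are seen, and the bias is about −1.9 and −2.5.
- All dropouts leave before the first post-baseline image: e = 0 and the bias is 0.
- Baseline medians from 5 to 11 mm²: −1.0 to −1.3 at Week 48 and −1.1 to −2.4 at Week 96.
- Ceiling without distributional assumptions: irreversibility gives e ≤ m(1−p), so the shortfall is at most pm(1−p)/(1−mp). At the worst p this is 4.1 points for m = 15% and 7.2 for m = 25%.

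**Treatment contrast.** With equal dropout and each patient's growth multiplied by 0.8, the odds ratio is 1.484 in truth and 1.490 under the rule at Week 48, and 1.456 and 1.467 at Week 96. With identical arms and random dropout of 13%/22% (Weeks 48/96) in one and 17%/28% in the other, the rule creates a difference of 0.4 and 0.6 points, against a standard error of 3.3–4.2 points.

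**The case against.** **The text is not open-ended.** The defaults in Sections 4.5 and 4.5.3 settle the unnamed patients: they are left out. This stands, and it is the reading adopted here. A reader might infer that the plan leaves a free choice, to be made once the data are seen, between understating the rate and overstating it by 6 to 11 points. The documents do not support that. The alternative reading credits unobserved patients with success against an explicit no-imputation default, and rests on the words about inclusion detached from their condition. Its figures also shrink: to about +4.5 and +9 if every dropout has an early-termination image, and to about +1.7 and +5.5 if patients with no post-baseline image are left out under the Section 4.5 general rule ((0.374 + 0.124 − 0.075)/0.925 = 45.7%; (0.148 + 0.160 − 0.075)/0.925 = 25.2%).

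**Completely random dropout is the least favourable comparison for the rule.** If fast progressors leave more often, keeping their known failures helps. With dropout odds doubled per SD of growth, the rule's bias is about +1.1 at Week 48 and close to zero at Week 96, against about +3.3 and +3 for plain observed cases. If slow progressors leave more often (odds × 0.67), the rule is worse: −2.7 and −3.7, against −1.7 and −1.9. This stands. It is why plain observed cases are not recommended as the main analysis.

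**The endpoint is exploratory and gates nothing.** This also stands, and it limits the grade of the point.

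**Conclusion.** The point holds as a modest flaw in an exploratory analysis. Read with the observed-data defaults, the rule makes inclusion depend on the outcome and understates the per-arm proportion under completely random dropout. The shortfall is about 1.3 points at Week 48 and 2.1 at Week 96 in the central case.

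The direction follows from the rule. The size rests on an assumed baseline distribution and dropout timing, and at Week 96 on a dropout rate borrowed from microperimetry. It would be wrong to say that the rule always biases the rate: there is no bias if no failure is observed before dropout, and under dropout related to fast growth the rule can lie closer to the truth than observed cases.

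With equal dropout the treatment odds ratio hardly changes. No primary or key secondary conclusion is affected. The percent-change analysis in Section 4.5.1.5 addresses relative growth on a continuous scale, but does not correct this proportion.

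**What to change.** In SAP Section 4.5.3:

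- Keep the carry-forward of an observed ≥20% increase.
- For the other missing patients, interpolate intermittent gaps and multiply impute GA area under MAR as in Section 4.5.1.4 (visit-to-visit differences, by treatment arm and biomarker status), extended to Weeks 72 and 96. Then dichotomise.
- State that this includes patients with a baseline but no post-baseline image, as an exception to the general rule in Section 4.5.
- Report plain observed cases as a sensitivity analysis.

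Predictive mean matching is an option, not a requirement. In simulated trials with 312 patients per arm it left a bias within about 0.2 points at both visits. Regression with normal errors left −0.7 to −0.3 at Week 48 and −0.2 to +0.5 at Week 96.

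The cost is a short SAP edit, modest programming and reliance on MAR; no new data are needed. The gain is about 1 to 2 points in the per-arm rate, and less if fast progressors leave much more often. If the present rule is kept, the minimum repair is one clause saying how a missing patient without an earlier failure is handled.

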4.5.4 Additional Biomarker Analyses

Additional biomarker-related analyses will be performed as specified below:

- Analysis of biomarker prognostic effects:
 - For patients in the sham treatment group, a comparison of change from baseline in GA area between biomarker-positive patients and biomarker-negative patients will be performed to evaluate the prognostic value of the CFI-profile biomarker using a similar model as the primary analysis.
- Analysis of potential association of genetic variants in CFI and complement pathway genes with disease characteristics and response to administration of lampalizumab
 - Patients with rare coding variants in CFI will be identified by sequencing and a modified exploratory analysis will be conducted in which all rare coding variant carriers are combined with CFI-profile biomarker-positive to define an exploratory "CFI-profile plus rare variant" biomarker-positive subgroup. For this exploratory analysis, the primary efficacy analysis as described in Section 4.5.1 (including predictive and prognostic aspects) will be performed, but using this modified exploratory biomarker definition.

- A pre-specified set of SNPs associated with complement-related genes will be evaluated using multivariate statistical methods for an exploratory evaluation of genetics associated with disease characteristics and/or lampalizumab treatment response. Detailed methods will be described separately in an Exploratory Genetic Analysis Plan that will be finalized prior to Sponsor unmasking for the analysis of the primary efficacy endpoint. Given the exploratory nature of these analyses, the results may not be included in the CSR.

4.6 PHARMACOKINETIC AND PHARMACODYNAMIC ANALYSES

The PK analyses will include all randomized patients who have at least one serum and/or aqueous humor PK sample, with patients grouped according to treatment actually received. Lampalizumab concentrations in serum and aqueous humor, as well as complement factor D levels (PD) in aqueous humor will be summarized by timepoint using descriptive statistics. Noncompartmental analysis may be performed with serum PK as appropriate.

Additional PK and exposure-response analyses may be conducted as appropriate. Population PK and PK/PD modeling may be performed to characterize the lampalizumab pharmacokinetics, GA area dynamic over time with and without lampalizumab treatment, and their associated variability, with results reported separately from the CSR. A separate modeling and simulation analysis plan will be prepared prior to any analysis.

4.7 SAFETY ANALYSES

The safety profile of lampalizumab will be assessed through the summary of adverse events, deaths, laboratory results for alternative complement pathway activity, serial ECG results, incidence of anti-drug antibodies, and ocular assessments (e.g., intraocular pressure [IOP]).

At the time of the Week 48 primary efficacy analysis, safety summaries will be produced based on the complete Week 48 data. In addition, summaries for ongoing second year safety data (after Week 48 and up to a single specified clinical cutoff date) will also be produced. At the time of the final analysis, safety summaries will be produced based on cumulative Week 96 data.

Safety outcomes will be summarized based on the safety-evaluable population or ECG-analysis population as appropriate, with patients grouped according to the treatment actually received (see Sections 4.1.2 and 4.1.4).

